#### 5 ENDPOINTS AND COVARIATES

Descriptive summary tabulations will describe the demographic, clinical characteristics as well as pre-existing comorbidities of the patients in the study population at the time of PAXLOVID™ prescription, and Healthcare Resource Use during the 30 days post index date.

#### 5.1 PRIMARY ENDPOINT

This study focuses on the patients who have received PAXLOVID™ for COVID-19 infection. The primary endpoints that describe the primary objectives in the study population will be:

- The baseline demographics (age, gender, ethnicity, education, employment status), clinical characteristics (height, weight, BMI, smoking status, pre-existing comorbidities), concomitant medications at index date and previous COVID-19 infection during the last 6 months, duration between last infection and index date, of the study population at the time of PAXLOVIDTM prescription.
- COVID-19 vaccination history (Receipt of vaccination (yes/no), type of vaccine, duration between vaccination and Index date), number of doses, at the time of PAXLOVIDTM prescription.
- Nirmatrelvir, Ritonavir prescription (total dose of Nirmatrelvir/Ritonavir, dose of Nirmatrelvir, dose of Ritonavir, Frequency of dose, dispensed amount) at the time of PAXLOVIDTM prescription.

PFIZER CONFIDENTIAL CT24-WI-GL03-RF03 2.0 Non-Interventional Statistical Analysis Plan 01-Jun-2020 Page 16 of 42

- Medications used to treat COVID-19 infection (Antiviral, Antiviral, Steroid, Antithrombotic, Monoclonal antibody, Hydroxychloroquine and Other medications) at the time of PAXLOVID™ prescription.
- HCRU characteristics in terms of patient hospitalization status, COVID-19 related hospitalization, length of days in the hospitalization due to COVID-19, Intensive care unit (ICU) admission and length of stay in the ICU due to COVID-19, supplemental oxygen use, vasopressor use, patient intubation, outpatient visits and ER Visits due to COVID-19 at the time of PAXLOVIDTM prescription.

#### 5.2 SECONDARY ENDPOINT

- HCRU characteristics in terms of patient hospitalization status, COVID-19 related hospitalization, length of days in the hospitalization due to COVID-19, Intensive care unit (ICU) admission and length of stay in the ICU due to COVID-19, supplemental oxygen use, vasopressor use, patient intubation, outpatient visits and ER Visits due to COVID-19 during the 30-day post-index period.
- COVID-19 PCR and/or antigen test result(s), PCR test result(s), Antigen test result (s), Duration to negative COVID-19 test during the 30 days post-index period.

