#### Rationale

The COVID-19 pandemic has exacerbated healthcare systems globally, with dire repercussions on patients, healthcare infrastructure, resources, and finances. Although COVID-19 patient characteristics and disease course in healthcare settings have been described in the literature since the beginning of the pandemic in various regions including the USA, EU, and the MENA region; there is limited data related to COVID-19 patient characteristics, treatment patterns, and HCRU identified in an outpatient setting, particularly in the MENA region. One study reported that among other factors such as age, male gender, and underlying medical conditions; being of Arab ethnicity was associated with increased risk of severe COVID-19 and related mortality.

In KSA, nirmatrelvir, ritonavir has been approved and conditionally registered by the Saudi Food and Drug Authority (SFDA) for patients aged  $\geq 12$  years, weighing  $\geq 40$  kg with mild-to-moderate COVID-19 symptoms and at high-risk for progression to severe COVID-19 infection. The availability of antiviral therapies such as nirmatrelvir, ritonavir in an outpatient setting has the ability to reduce disease progression, hospitalization, and COVID-19-related mortality, when eligible patients are treated. With the current EU authorization and subsequent use of nirmatrelvir, ritonavir, there is a need to generate -RWE during this early EUA utilization phase to inform decision-making on national levels.

PFIZER CONFIDENTIAL CT24-WI-GL03-RF03 2.0 Non-Interventional Statistical Analysis Plan 01-Jun-2020 Page 9 of 42 As such, this study aims to describe the baseline demographic, clinical characteristics, and HCRU of adult COVID-19 patients who have been prescribed nirmatrelvir, ritonavir treatment in KSA.

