#### 3.1.3 Exclusion Criteria

There are no exclusion criteria for this study.

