#### Table 1.Data Collection Schedule

COVID-19: Corona Virus Disease 2019 caused by SARS-CoV-2; HCRU: Healthcare Resource Use.

a Cohort 1/Cohort 2: Index date is defined as the date of nirmatrelvir, ritonavir prescription.

b Cohort 1: Post-index period is defined as the 30-day period after the index date and prior to the site initiation date.

*c* Cohort 2: Post-index period is defined as the 30-day period after the index date and after the site initiation date.

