#### 3.2.2 Secondary objective:

*To assess adult COVID-19 patients' HCRU within the 30-day period following nirmatrelvir, ritonavir prescription, including:* 

• Overall HCRU in inpatient and outpatient settings.

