#### 4.2 SUBGROUPS

*Exploratory stratifications will be conducted, as appropriate and where the sample size permits, to explore differences by:* 

- *Age groups: 18–49, 50–64, 65–74, ≥75 years of age;*
- Gender;
- *BMI categories:* (<18.5 = underweight, 18.5−24.9 = normal, 25−29.9 = overweight, ≥30 = obese);
- *Smoking status;*
- *Medications used to treat COVID-19 in addition to nirmatrelvir, ritonavir;*
- *Previous COVID-19 infection;*
- COVID-19 vaccination history;
- *Nirmatrelvir, ritonavir treatment completion (if available)*
- Days from COVID-19 diagnosis to nirmatrelvir, ritonavir index date;
- Days from prescription to dispensing (if available).
- Days from COVID 19 symptoms onset to dispensing (if available).
- Days from COVID 19 symptoms onset to nirmatrelvir, ritonavir prescription (if available).

For each stratification variable, the full analysis set will be segmented into nonoverlapping subgroups based on the stratification variable values. The stratifications may not be meaningful, if there are no patient's data in some of the groups or there are many variables with a lot of missing data.

The exploratory stratifications will be conducted for the following study objectives if enough data are available:

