#### 6 HANDLING OF MISSING VALUES

Should missing data occur, the data will be analyzed as they are recorded in the eCRFs, and no imputation of missing data will be performed. The number of missing values for data elements will be reported.

All data analysis in this study will be performed on the Full Analysis Set containing all patients who fulfil the eligibility criteria, and thus missing data is not used as criteria for excluding the patients from the data analysis.

For both categorical and continuous variables, the amount of missing data will be reported. For categorical variables, the missing values will be analysed in the descriptive summary tables as a category. The missing values in the continuous variables will be ignored when calculating the summary statistics of mean, median, standard deviation, and quantiles.

If some of the variables of interest show to have a large amount or proportion of missing data, the summary statistics of the variable to be interpreted accordingly.

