# Secondary analysis: To assess adult COVID-19 patients' HCRU within the 30-day period following nirmatrelvir, ritonavir prescription, including: Overall HCRU in inpatient and outpatient settings.

Healthcare Resource Use (HCRU) data will be summarized using descriptive statistics in terms of patient hospitalization, number of time patient hospitalization, cause of patient hospitalization, length of stay in the hospitalization, Intensive Care Unit (ICU) admission,

PFIZER CONFIDENTIAL CT24-WI-GL03-RF03 2.0 Non-Interventional Statistical Analysis Plan 01-Jun-2020 Page 19 of 42 number of Intensive Care Unit (ICU) admission, length of stay in Intensive Care Unit (ICU), supplemental oxygen use, type of oxygen, vasopressor use, patient intubation, outpatient visits, number of outpatient visits and reason of outpatient visits during the 30 days post index date and reported as shown in the *Table Shell 9*. Further stratification will be performed as described in section 3.2.

COVID-19 PCR and /antigen test result(s), Result(s) by PCR only, Result(s) by antigen test only, duration to COVID-19 negative result(s) by PCR and/antigen tests from the index date will be reported will be reported as shown in the *Table shell 21*.

COVID-19 variant by following stratifications will be reported as shown in the *Table shell 22.1 to 22.7: (if sample size permits)* 

- Age groups: *Table shell 22.1*
- Gender: *Table shell 22.2*
- BMI categories: *Table shell 22.3*
- Smoking status: *Table shell 22.4*
- Previous COVID-19 infection: *Table shell 22.5*
- COVID-19 vaccination history: Table shell 22.6
- Underlying medical conditions: Table shell 22.7

Duration to COVID-19 negative result(s) by following stratifications will be reported as shown in the *Table shell 23.1 to 23.10: (if sample size permits)* 

- Age groups: *Table shell 23.1*
- Gender: *Table shell 23.2*
- BMI categories: *Table shell 23.3*
- Smoking status: *Table shell 23.4*
- Previous COVID-19 infection: *Table shell 23.5*
- COVID-19 vaccination history: *Table shell 23.6*
- Underlying medical conditions: Table shell 23.7
- Medications used to treat COVID-19 in addition to nirmatrelvir, ritonavir: *Table shell 23.8*
- Days from COVID-19 diagnosis to nirmatrelvir, ritonavir index date: *Table shell* 23.9
- Days from prescription to dispensing (*if available*): *Table shell 23.10*

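### The 30-day HCRU table pools patients already in hospital at prescription with those who were not, so it does not show new hospitalisation after prescription; one extra split would

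*SAP*

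**What the plan says.** The secondary objective (SAP 3.2.2) is HCRU in the 30 days after prescription, specified as "Overall HCRU in inpatient and outpatient settings". SAP 5.2 lists the post-index items, beginning "HCRU characteristics in terms of patient hospitalization status, COVID-19 related hospitalization, length of days in the hospitalization due to COVID-19". SAP 5.1 lists the same items at the time of prescription as a primary endpoint.

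On who is included, SAP 3.1.3 states "There are no exclusion criteria for this study", and section 6 states "All data analysis in this study will be performed on the Full Analysis Set containing all patients who fulfil the eligibility criteria". For the strata, 4.2 says that "the full analysis set will be segmented into nonoverlapping subgroups based on the stratification variable values".

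The plan provides for patients in hospital at index. SAP 7.2 tabulates hospitalisation, ICU stay, oxygen and intubation at index (Shell 8), 7.3 repeats this by six characteristics (Shells 8.1 to 8.6), and 7.3 item 3 models COVID-19 hospitalisation at index.

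For the 30 days after index, 7.2 describes Shell 9 as covering hospitalisation yes/no, "number of time patient hospitalization, cause of patient hospitalization, length of stay in the hospitalization", ICU use and other items. Annex Table 2 defines an Outpatient setting variable as a No to the hospitalisation question. It appears in the index block and again among the post-index rows, with the index date as time point both times.

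**The concern.** A percentage hospitalised in the 30 days after a prescription is easily read as what happened to patients after they were prescribed the drug. That reading needs patients who were outside hospital at the start. Here the denominator also holds patients already admitted. If a stay under way at index is recorded as a post-index hospitalisation, the numerator mixes continuing and new stays. If it is not, the denominator still contains people who could not be newly admitted while that stay lasted. Neither convention gives the risk of new admission among those at risk of it.

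The objective names inpatient and outpatient settings, and the SAP rationale says "there is limited data related to COVID-19 patient characteristics, treatment patterns, and HCRU identified in an outpatient setting". A table that keeps the two groups apart would serve both statements better than a pooled column alone. Differences between strata in Shells 10 to 20 may also partly reflect who was already in hospital.

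**Working it through.** The documents give no admission rate, inpatient share or precision target, so there is no stated figure to reproduce. The check has a textual part and an illustrative part.

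**Is there a split or a rule in the text?**
- The strata in SAP 4.2 are age, gender, BMI, smoking, other COVID-19 medication, previous infection, vaccination, treatment completion and four timing variables. Hospital status at index is not among them.
- The ad hoc strata in 7.1 are demographics and underlying conditions.
- The titles of Shells 9 to 20 cover the whole population or one of the 4.2 strata. Shells 24 and 24.1 name hospitalisation at index, but as a regression outcome.
- For Cohort 1, the Table 1 footnote says "Post-index period is defined as the 30-day period after the index date and prior to the site initiation date". This fixes the window and does not say how a stay that began before it is coded.
- Annex Table 2 has post-index rows for hospitalisation (Yes/No), cause and length of stay, with no visible rule for a stay already under way.

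**Can Shells 8 and 9 be combined?** Let A be the number hospitalised at index, B the number recorded as hospitalised post-index, and n the total. The number with index No and post-index Yes lies between B − min(A, B) and B − max(0, A + B − n). Take n = 250 (the SAP 3.1 target) and assume A = 50 and B = 60:
- lower limit: 60 − 50 = 10
- upper limit: 60 − max(0, 110 − 250) = 60
- out of 200 index outpatients: 5% to 30%

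These are logical limits. The upper one needs all 50 index inpatients to be coded No post-index. Subtracting A from B is correct only if every one of them is coded Yes, which no visible passage states.

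**How far can the pooled figure lie from the new-admission figure?** All inputs are assumptions: q is the share in hospital at index, r the new-admission risk among the rest, c the share of index inpatients still in hospital after index, and s readmission among index inpatients.
- Ongoing stays counted: (1 − q)r + q[c + (1 − c)s]
- Ongoing stays not counted: (1 − q)r + qs

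With r = 5%, c = 1 and s = 0:

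| q | Counted | Not counted | Index outpatients |
|---|---|---|---|
| 5% | 0.0475 + 0.05 = 9.8% | 4.8% | 5% |
| 10% | 0.045 + 0.10 = 14.5% | 4.5% | 5% |
| 20% | 0.04 + 0.20 = 24.0% | 4.0% | 5% |
| 30% | 0.035 + 0.30 = 33.5% | 3.5% | 5% |

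Variations at q = 20%: if half are still in hospital (c = 0.5, s = 0), 14.0% against 4.0%; with c = 1 and s = 5% or 10%, 24.0% against 5.0% or 6.0%. The index-outpatient figure stays at 5% throughout; at q = 20% it is 10/200, Wilson 95% CI 2.7% to 9.0%.

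**The case against.** The strongest reply is that the plan never sets new admission as an endpoint. It sets overall HCRU among all adults prescribed the drug, in a descriptive study without a hypothesis (Protocol 9.6). The rationale's remark on outpatient settings describes a gap in the literature and does not restrict the population. This stands: a reader might infer that the pooled 30-day figure is wrong, and the documents do not support that. It is a valid answer to the objective as written.

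Second, the split may already exist. The repeated Outpatient setting row beside the post-index items is consistent with a setting split inside Shell 9, though it could be a copying slip. The shell layouts are in a separate Excel file (SAP section 2, version 2.0), and Protocol 9.10 mentions eCRF completion guidelines. Neither was available. The separate index row for length of stay may also bear on how ongoing stays were recorded. So absence can be asserted only for the visible text and the shell titles.

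Third, the size rests wholly on assumed inputs. That 7.3 models index hospitalisation on seven covariates does not show that it is common. The background describes use in adults not requiring hospitalisation, which points to a small share; SAP 3.1.1 says the sites treat complicated patients. The share is unknown.

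Fourth, a reader might infer that every stratified table needs the same split. Shells 8.1 to 8.6 already show index hospitalisation for the characteristics in Shells 10 to 13, 15 and 16, and Shell 8.5 partly covers 15.1. Numbers would also be thin. An average age stratum has 250/4 = 62.5 patients; at q = 20% about 50 are index outpatients, and 2/50 has a 95% CI of 1.1% to 13.5%. That split is a debatable trade-off and should not be required.

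**Conclusion.** The point holds as a cheap improvement of minor severity. As listed, the 30-day summary combines patients in hospital at prescription with patients who were not. It therefore does not give new hospitalisation after prescription, and the index and post-index tables together give only limits on it. The conclusion is the same under either coding of ongoing stays. It rests on the visible SAP text and shell titles, and would fall away if the shell bodies already contain the split. A coding rule in the eCRF guidelines would need only to be cited.

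The size cannot be stated from the documents. The illustration shows that the pooled figure can sit well above the index-outpatient figure if ongoing stays count, and somewhat below it if they do not. It does not show that either happened here.

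**What to change.** In SAP 7.2 and Shell 9, keep the pooled column as overall HCRU and add columns by hospitalisation at index (Yes/No, from the item already captured). Report new post-index hospitalisation with patients not hospitalised at index as the denominator. Mark the split as added after analyses were performed, since section 2 records that completed analyses had already influenced version 2.0. Footnote how stays ongoing at index and admissions on the index date itself were coded. For Shells 10 to 20, a footnote that differences between strata may reflect hospital status at index is enough. If the shells or the eCRF guidelines already hold the split or the rule, cite them.

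The cost is SAP and shell wording and slightly more programming. The split columns hold smaller groups (200 and 50 in the 20% illustration), and same-day admissions coded as index Yes fall outside the new-admission figure. Data collection was planned to end on 01 February 2024 (Protocol section 6), so the coding footnote can only document past practice and cannot harmonise entries already made.

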#### 5.3 COVARIATES AND VARIABLE DEFINITIONS

Table 2 depicts patient demographics, clinical characteristics, COVID-19 vaccination history, nirmatrelvir, ritonavir prescription data, COVID-19 infection, HCRU variables and Detailed operational definitions of variables.

Variables and detailed definitions of the variables are provided in Table 2.

#### 6 HANDLING OF MISSING VALUES

Should missing data occur, the data will be analyzed as they are recorded in the eCRFs, and no imputation of missing data will be performed. The number of missing values for data elements will be reported.

All data analysis in this study will be performed on the Full Analysis Set containing all patients who fulfil the eligibility criteria, and thus missing data is not used as criteria for excluding the patients from the data analysis.

For both categorical and continuous variables, the amount of missing data will be reported. For categorical variables, the missing values will be analysed in the descriptive summary tables as a category. The missing values in the continuous variables will be ignored when calculating the summary statistics of mean, median, standard deviation, and quantiles.

If some of the variables of interest show to have a large amount or proportion of missing data, the summary statistics of the variable to be interpreted accordingly.

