#### 6. MILESTONES

Milestone	Planned date
Start of data collection	01 July 2023
Interim report 1*	01 October 2023
End of data collection	01 February 2024
Final Study Report	01 November 2024

\*If the target sample size is achieved from Cohort 1 (and Cohort 2 is not initiated), then the interim analysis will not be required.

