#### PFIZER CONFIDENTIAL

CT24-WI-GL02-RF02 4.0 Non-Interventional Study Protocol Template For Secondary Data Collection Study 01-Jun-2022 Page 22 of 34

- Completed eCRFs.
- Documentation of adverse events (AEs), and transmission of serious adverse events (SAEs).
- Identification of patients lost to follow-up.
- Study correspondence.
- Compliance with Institutional review board (IRB)/Independent ethics committee (IEC) approval requirements.
- Review of the ISMF.
- Archiving of the study documents will be performed according to Pfizer standard operating procedures (SOPs).

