#### Cohort 2:

If the minimum target sample size of 250 patients is not achieved from Cohort 1, then a second Cohort of patients (Cohort 2) will be initiated and will be included in the study until the target sample size is met. Cohort 2 patients are those who meet the eligibility criteria (see Section 3.1.2), and who have been prescribed nirmatrelvir, ritonavir treatment after the date of site initiation. As for patients in Cohort 1, the following data will be collected for patients in Cohort 2: demographics and clinical characteristics at index date, and HCRU during the 30day period post-index date.

Patients in Cohort 1 will be enrolled in the study in a consecutive manner from start of site initiation till lookback period until we reach desired sample size, in case the number of eligible patients is significantly larger than the sample size. For Cohort 2, patients will be enrolled in the study in a consecutive manner from start of site initiation until we reach desired sample size. *An electronic Case Report Form (eCRF) will be available for* 

PFIZER CONFIDENTIAL CT24-WI-GL03-RF03 2.0 Non-Interventional Statistical Analysis Plan 01-Jun-2020 Page 10 of 42 the selected sites to fill in for each patient included in Cohort 1 or Cohort 2. Patient data will be extracted from the medical records and entered into the eCRFs by trained site study personnel. Participation in this study is not intended to change the routine treatment patients receive, as determined by their prescribing physicians; all treatment decisions, type and timing of the disease monitoring are per routine clinical care, and at the discretion of the treating physician and patient.

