#### 3.1.2 Inclusion Criteria

Patients must meet all of the following inclusion criteria to be eligible for inclusion in the study:

- 1. Confirmed COVID-19 infection during the study observation period.
- 2. Age  $\geq 18$  years old.
- 3. Nirmatrelvir, ritonavir written prescription.

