#### 7 STATISTICAL METHODOLOGY AND STATISTICAL ANALYSES

#### 7.1 STATISTICAL METHODS

This is a descriptive study, and as such, no statistical testing will be conducted. Analyses will be conducted using Statistical Analysis System (SAS) (version 9.3 or higher). Summary statistics for patient demographics, clinical characteristics, treatment patterns, and patient HCRU will be performed. Continuous variables will be summarized using standard summary statistics such as number of observations (n), mean, median, standard deviation (SD), first and third quartile, minimum and maximum value. Categorical variables will be summarized in frequency tables as counts and proportions of the total study population, and by subgroups where appropriate. The proportion of missing data will be reported for each variable.

Ad hoc population analyses would include stratification by demographic characteristics and presence of Underlying Medical Conditions Associated with Higher Risk for Severe COVID-19.

All patients who fulfill the study eligibility criteria will be included in the data set for analyses.

One interim analysis will be conducted after 3 months of recruitment only if the target sample size is not achieved from Cohort 1 i.e. Cohort 2 is initiated.

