#### Limitations and Bias

As this is a retrospective observational study and participant enrolment in the study will be done in a consecutive manner. This approach is associated with low possibility of bias and representativeness of the enrolled sample could be affected, if there is pattern observed among a particular age group or due to any season etc. In case such selection bias is observed, then additional stratification/ subgroup can be reported in the analysis, as required.

Since this study will involve collection of existing data from medical records, misclassification bias due to recording errors is possible. Medical records may not always be complete, the availability and quality/completeness of data may vary

> PFIZER CONFIDENTIAL CT24-WI-GL03-RF03 2.0 Non-Interventional Statistical Analysis Plan 01-Jun-2020 Page 23 of 42

considerably between different sites within KSA, and there may be abstraction errors and differences in reporting standards between the different sites.

Another limitation to be considered is the characteristics of the patient population to be included in the final analysis, which may potentially be biased based on the KSA national recommendations put in place for the management and treatment of COVID-19 during the observational period. This may affect the generalizability of findings from this study across different countries in the real-world setting.

At the patient-level, misclassification of drug exposure has to be considered. Medical records provide detailed information on patient demographics, clinical characteristics, and prescribed nirmatrelvir, ritonavir treatment, but may not contain information on the intended duration of use (days of supply) and may not contain accurate information on the actual treatment pattern of nirmatrelvir, ritonavir medications by the patient ie, patient adherence (if any).

COVID-19 outcomes are dependent on individuals seeking healthcare i.e., individual may have symptoms for long but if there is not an interaction with the health system, it will be unknown.

Number	Description					
Table shells for P	Table shells for Primary objectives					
Table shell 1	Summary of patient enrolment at Index date.					
Table shell 2	Summary of demographic characteristics of patients at Index date.					
Table shell 3	Summary of clinical characteristics of patients at Index date.					
Table shell 4	Summary of COVID-19 vaccination history of patients at Index date.					

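### 30-day resource use is tabulated on every eligible patient with no rule that 30 days were observable, although the Cohort 1 window stops at site initiation and Cohort 2 has no last index date

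*SAP*

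**What the plan says.** **Who is analysed.** SAP section 6: "All data analysis in this study will be performed on the Full Analysis Set containing all patients who fulfil the eligibility criteria". SAP 3.1.1 assesses eligibility at the index date. The criteria in 3.1.2 are confirmed infection, age and a "Nirmatrelvir, ritonavir written prescription". SAP 3.1.3 adds: "There are no exclusion criteria for this study". None of these concerns how long the record runs after index.

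**How use is summarised.** Protocol Table 3 and SAP Annex Table 2 record hospitalization, ICU admission, oxygen, vasopressors, intubation, outpatient visits and ER visits as occurred or not. SAP 7.1 takes proportions over the total study population. SAP section 6 shows missing categorical values as a category of their own and does not impute.

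**The window.** In SAP Table 1 (Protocol Table 4), footnote b gives the Cohort 1 post-index period as the 30 days after index that also precede site initiation. SAP 3.1 describes a 15-month lookback from site initiation, with index dates from 01 April 2022 to 30 June 2023. When eligible patients clearly exceed the target, Cohort 1 is enrolled consecutively from site initiation into the lookback.

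**Cohort 2.** It opens only if Cohort 1 falls short of 250, and "will be initiated and will be included in the study until the target sample size is met". No last index date is given. SAP 7.1 adds: "One interim analysis will be conducted after 3 months of recruitment only if the target sample size is not achieved from Cohort 1". Protocol section 6 puts the interim report at 01 October 2023 and the end of data collection at "01 February 2024".

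**Source.** Medical records at three sites, with no linkage to other providers described.

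**The concern.** 30-day resource use is the only secondary objective, and Table Shells 9 to 20 all report it. A 30-day proportion means what it says only if each patient in the denominator could be followed for 30 days, or if shorter follow-up is handled explicitly. The plan does neither. Followed as written, it places patients with fewer than 30 observable days in the denominator at full weight.

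Use after the window closes, or at another provider, then lowers the reported proportion whichever way it is handled. Recorded as No, it counts as no use. Left blank, it appears as missing but still sits in the denominator. The result would be read as overall 30-day use in treated patients, when part of that use could not have been seen.

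**Working it through.** The target of 250 is set by feasibility, with no precision or power inputs, so there is no sample-size figure to reproduce. The one plan figure that can be checked agrees: 01 April 2022 to 30 June 2023 is 15 calendar months, or 456 days.

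**Inputs.** Lookback dates: SAP 3.1. Window limit: SAP Table 1, footnote b, read as a cap. Milestone dates: Protocol section 6. Assumptions: site initiation on 01 July 2023 (the planned start of data collection, and the day after the lookback ends), index dates spread evenly, and a true 30-day use of 10%.

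**Cohort 1 window.** Observed days = min(30, days after index and before initiation).
- Index 31 May 2023: 30 days, complete.
- Index 01 June: 29 days. Index 30 June: 0 days.
- Mean over June: (29 + 28 + … + 0)/30 = 14.5 days.
- Share of the lookback: 30/456 = 6.6%, or 0.066 × 250 ≈ 16 patients.

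With initiation on 15 July the share is 16/456 = 3.5%; on 01 August it is 0.

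**Effect on the proportion.** The tabulated value is the average over patients of the chance that use falls in the observed days. Two timings were tried: constant hazard, λ = −ln(1 − 0.10)/30; and front-loaded, F(t) = (1 − e^(−t/7))/(1 − e^(−30/7)). As a rough check for constant hazard: 10% × (1 − 0.066 × 15.5/30) ≈ 9.7%.

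If SAP 3.1 is read as taking the most recent patients first, 250 out of N eligible patients come from the last 456 × 250/N days (N is assumed):

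| N eligible | Days used | Short windows | Patients of 250 | True 10%: constant hazard / front-loaded |
|---|---|---|---|---|
| 250 | 456 | 6.6% | 16 | 9.7% / 9.8% |
| 500 | 228 | 13% | 33 | 9.3% / 9.7% |
| 1000 | 114 | 26% | 66 | 8.7% / 9.4% |
| 2000 | 57 | 53% | 132 | 7.3% / 8.8% |

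**Cohort 2, only if opened, with even accrual from 01 July 2023.**
- Interim at 01 October: 30/92 = 33% of Cohort 2 have incomplete windows, and 10% is tabulated as 8.3% within Cohort 2 (constant hazard).
- At 01 February 2024: at most 30/215 = 14%, since accrual stops once the target is met. Within Cohort 2, 10% × (1 − 0.14 × 15.5/30) ≈ 9.3%. If Cohort 2 were 20% of all patients (assumed) and Cohort 1 complete, the overall figure is 0.2 × 9.3 + 0.8 × 10 ≈ 9.9%.

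**Care elsewhere.** If a share q of users is seen only at other providers, the tabulated value is 10% × (1 − q). For an assumed q of 5% to 30% this gives 9.5% to 7.0%. The documents give no value for q, so this shows direction, not size.

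**The case against.** The strongest reply is that the SAP has a missing category, reports the amount missing and forbids imputation, so an unobserved item would appear as missing. A reader might infer that unobserved days are coded as No. **The documents do not support that:** no passage tells sites to do so, and the eCRF completion guidelines are not among the documents. The missing category still does not remove the problem. A chart seen for 12 of 30 days with no admission need not leave a blank, and a missing value remains in the total-population denominator.

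Two further stronger readings also fail. SAP section 8 says of outcomes: "if there is not an interaction with the health system, it will be unknown". That sentence concerns people who do not seek care; for resource use, someone with no contact used none, so it is not evidence of miscoding. Protocol 9.9 lists "Identification of patients lost to follow-up", but among checks at on-site visits that are made only if necessary. It does not show that the eCRF lacks such a field.

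It is also fair to say that the Cohort 2 figures are doubly conditional and are shares of Cohort 2, not of the analysis set. Lowering the target to 250 makes that cohort less likely to be needed. SAP Table 1 does schedule resource use over the 30-day period for both cohorts, but a schedule does not make the days observable. Finally, footnote b could be read as requiring all 30 days to precede initiation. With initiation at the end of the lookback, it would then conflict with index dates to 30 June 2023, so reconciliation is needed on either reading.

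**Conclusion.** The point holds in a limited form. The plan has no observability requirement for the 30-day tables, and its own window definition and lookback dates produce short windows if initiation was near 01 July 2023. The bias is downward and probably small: about 0.3 percentage points on a true 10% over the whole lookback under constant hazard, and less if use is front-loaded. It grows if eligible patients far exceed 250 and the most recent are taken first, and it is zero for Cohort 1 if initiation was 01 August. These figures rest on the assumed initiation date, even spread of index dates, and footnote b acting as a cap.

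Use at other providers is a separate, unstated limitation of unknown size. It would be wrong to conclude that the results are seriously understated; the documents give no basis for a large figure.

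**What to change.** 1. Reconcile footnote b (SAP Table 1, Protocol Table 4) with the lookback dates. Either let the 30-day window run past site initiation, or limit Cohort 1 to index dates whose 30 days all precede it (up to 31 May 2023 if initiation was 01 July).
2. State in SAP 4.1 and 7.1 that Table Shells 9 to 20 use patients whose full 30-day window falls before the record cut-off. Define this by calendar dates only, so that patients who die within 30 days stay in. Report how many are left out, and show the Full Analysis Set version alongside.
3. Label the result as resource use recorded at the three study sites, and add care at other providers to SAP section 8.

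SAP 2.0 is dated 16 September 2024, after the planned end of data collection. The restriction needs only index dates and the cut-off date, so no chart has to be reopened. A new last-contact field is not proposed. Nor is a repeat analysis in patients seen on or after day 30, which would select on later healthcare use and drop early deaths.

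The cost is SAP wording and a second set of tables. A few late-indexed patients leave the main 30-day tables: about 16 of 250 over the whole lookback if the window stays capped at 01 July, more under most-recent-first sampling. The claim becomes narrower. Restricting the window does not repair missing care at other providers.
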